**PARTNERS HUMAN RESEARCH COMMITTEE
STATISTICAL ANALYSIS PLAN**

Title: Mechanisms of Pharyngeal Collapse in Sleep Apnea

Title of the study: Effect of Added Varnum Mouthpiece on Pharyngeal Collapsibility and Sleep Apnea Severity in Mouth Breathers

NTC: NCT02738255

PI Name: [name]

Protocol #: 2012P000957

Document Date: 02/01/2017

VI. BIOSTATISTICAL ANALYSIS

Part F (oral breathing):

Patients participating in the study are OSA patients with self-reported mouth breathing as well as nose breathers. They will be studied for baseline and device night in random order. The main outcomes are: 1. improvement in sleep apnea severity as quantified by apnea-hypopnea index, 2. improvement in pharyngeal collapsibility as quantified by peak airflow.

Power Calculations: We will plan to enrol 30 individuals. With an anticipated failure rate of 20% (due to insufficient sleep in the lab environment or difficulty tolerating the monitoring equipment, etc), this should yield a total of 24 subjects for analysis. We expect that 67% of the population will respond to this therapy, such that 16 patients will have improved sleep and reduced AHI. This sample size is designed to have >80% power to detect an effect size of $1.5 \times \text{S.D.}$ higher peak inspiratory flow (with device versus baseline). There is greater statistical power for the other comparisons.

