Test the effect of added a single-use Varnum mouthpiece on pharyngeal collapsibility and OSA severity in patients who identify themselves as mouth breathers. Research indicates that nasal breathing not only may improve sleep apnea but it also increases circulation, blood oxygen, and carbon dioxide levels, slows the breathing rate, and improves overall lung volumes (23).

Thus, we will test whether a single-use Varnum mouthpiece can improve pharyngeal collapsibility and OSA severity in mouth breathers. We will also test the Varnum mouthpiece in nose breathers to serve as a control for the effectiveness of the Varnum mouthpiece.

BACKGROUND AND SIGNIFICANCE

Provide a brief paragraph summarizing prior experience important for understanding the proposed study and procedures.

Obstructive sleep apnea (OSA) is characterized by repetitive pharyngeal collapse during sleep and is associated with increased morbidity and mortality. However, OSA remains undertreated due in part to the few treatment options available. Thus, understanding the pathophysiology of sleep apnea and developing novel therapies is of considerable importance. The mechanisms of recurrent upper airway collapse in OSA remain incompletely understood. Airflow limitation, negative effort dependence and progressive expiratory narrowing (defined below) are important characteristics of the upper airway associated with pharyngeal collapse that need further understanding.

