EEG, EMG, EKG, EOG, oxygen saturation, mask pressure, PETCO₂, and airway pressure will be performed the same as already described in part B. One of the following two procedures will be performed. 1) A non-rebreathing valve will be placed on the mask to enable changes in resistance to be made exclusively during expiration (providing expiratory pressure support) during sleep. 2) A single-use expiratory positive airway pressure (EPAP; Provent Sleep Therapy, Manchester, NH, USA) device will be applied to each nostril. The EPAP contains a mechanical valve with very low inspiratory resistance but low, medium, or high expiratory resistance with adhesive to provide a seal.

After instrumentation, the patients will be asked to sleep in the supine position with the chin forward.

Once asleep, during periods of reduced airflow (whether due to expiratory flow limitation or otherwise), expiratory resistance will be applied using the non-rebreathing valve (20-80 cmH₂O/L.s) in procedure 1 or the EPAP (low, medium, or high expiratory resistance) in procedure 2 to examine whether airflow increases. A sham expiratory resistance will operate as a control (turning the expiratory port towards a resistance of 0 cmH₂O). This data will allow us to test whether expiratory resistance increases airflow specifically in cases with expiratory flow limitation (rather than when expiratory flow limitation is absent).

Following completion of each study, all equipment will be removed, and the subject will be free to sleep in the laboratory free from equipment for the rest of the night. Alternatively, if the subject feels alert enough to leave, they may do so.

Study endpoints for Part E include successful completion of all measurements in the study, at the subject's request, or by discretion of the researcher.

Part F (oral breathing) (n=30):

Two overnight sleep studies, a baseline night and a device night, will be performed approximately one week apart in random order. On both baseline and device nights EEG, EMG, EKG, EOG, oxygen saturation, mask pressure, PETCO₂, and airway pressure will be performed the same as already described in part B. During the device night, in addition to these measurements, a single-use Varnum's mouthpiece, which is similar to an adhesive tape with a central opening, will be placed on a patient's mouth to encourage nasal breathing. The nostril-size central opening allows for oral breathing when necessary.

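### The SAP's claim of greater power for the other comparisons has no stated inputs and, on the plain reading of its 67% response figure, is false for AHI

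*SAP*

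**What the plan says.** The SAP, section VI (Biostatistical Analysis, Part F), names two main outcomes. The first is "improvement in sleep apnea severity as quantified by apnea-hypopnea index"; the second is pharyngeal collapsibility, measured by peak airflow. Each subject has a baseline night and a device night in random order, so the device comparison is paired.

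The Power Calculations paragraph starts from enrolment ("We will plan to enrol 30 individuals") and takes off 20% for failures, which leaves 24 for analysis. It then gives an expected response: "We expect that 67% of the population will respond to this therapy, such that 16 patients will have improved sleep and reduced AHI". The power claim follows: "This sample size is designed to have >80% power to detect an effect size of" 1.5 SD in peak inspiratory flow, device against baseline. The paragraph closes with "There is greater statistical power for the other comparisons".

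The SAP gives no alpha, sidedness or test. It does not say whether the SD is that of the paired difference or of the raw measurement. It gives no definition of response and no mean change or SD for AHI. The protocol's Part F text (Specific Aims; Research Design and Methods) does not supply these either.

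**The concern.** AHI comes first among the main outcomes but has no calculation of its own. Its only cover is the closing sentence, which ranks its power above that for peak flow. With the same 24 pairs and the same test, that ranking requires a standardised AHI effect larger than 1.5 SD. The one AHI figure in the SAP, the 67% response, looks much smaller than that if it is taken at face value.

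At stake is how a null AHI result would be read. A reader who trusts the closing sentence could take it as evidence of no effect from a well-powered comparison, when the SAP gives no basis for calling that comparison well powered.

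**Working it through.** **Inputs.** From the SAP: 30 enrolled, 20% failures, 24 analysed, 67% responding (16), 1.5 SD, power above 80%. The protocol's Part F heading also gives n=30. Assumed here because the SAP is silent: paired t-test, two-sided 5%, and SD meaning the SD of the paired difference, unless stated otherwise.

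**1. Sample-size chain.** 30 × (1 − 0.20) = 24, and 24 × 0.67 = 16.08, or 16. Both figures reproduce.

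**2. Peak-flow claim.** The power of a paired t-test is the probability that a noncentral t, with n − 1 degrees of freedom and noncentrality d√n, exceeds the critical value.

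- n = 24, d = 1.5: noncentrality 1.5 × √24 = 7.35; power 0.9999998.
- n = 6: 1.5 × √6 = 3.67; power 0.833. n = 5: power 0.711. Six pairs therefore suffice for 80%.
- n = 16, if the claim was meant for the 16 responders: power 0.99986.
- If the SD is the raw SD with night-to-night correlation ρ, then d = 1.5/√(2(1 − ρ)). At ρ = 0, d = 1.06 and power with 24 pairs is 0.9987.

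The claim of more than 80% holds on each of these paired readings, with a great deal to spare.

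**3. What 24 pairs can detect.** Setting power to 0.80 at n = 24 and solving gives d = 0.597, about 0.60 SD of the paired difference.

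**4. AHI from the 67%, plain reading.** If 67% have any reduction and paired changes are normal, d = Φ⁻¹(0.67) = 0.440. The noncentrality is 0.440 × √24 = 2.16 and power is 0.542. At two-sided 2.5% it is 0.419; at one-sided 5% it is 0.672. Reaching 80% at two-sided 5% would take 43 pairs (0.805).

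**5. Sensitivity to the response definition.** If a responder must improve by more than c (in SDs of the paired AHI change), then d = 0.440 + c:

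| Cut-off c | d | Power, 24 pairs |
|---|---|---|
| 0 | 0.44 | 0.54 |
| 0.16 (0.597 − 0.440) | 0.60 | 0.80 |
| 0.25 | 0.69 | 0.90 |
| 0.50 | 0.94 | 0.99 |
| 1.06 (1.5 − 0.440) | 1.50 | >0.9999, equal to peak flow |

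If instead responders improve by 1.0 SD and the rest by nothing, power is 0.81; with 1.5 SD in responders it is 0.97.

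**6. In terms of subjects.** Under normality, 80% power needs Φ(0.597) = 0.725 with any reduction, or 0.725 × 24 = 17.4 subjects. Matching 1.5 SD needs Φ(1.5) = 0.933, or 22.4 of 24, against the 16 stated.

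**7. If 1.5 SD is in raw units.** At ρ = 0 the peak-flow effect is 1.06 SD of the difference, so the AHI cut-off needed to match it falls to 1.061 − 0.440 = 0.62 SD. The plain-reading 0.44 SD is still below it.

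**The case against.** The strongest reply is that 67% is a planning expectation with no definition behind it. The SAP couples reduced AHI with improved sleep. If both are required, the share with reduced AHI alone could exceed 67%, and a non-responder could still have a small reduction. The table shows how little is needed: a cut-off of about 0.16 SD, or 17 to 18 subjects with any reduction instead of 16, brings AHI to about 80%. The 24 also include nose breathers. If AHI were tested in mouth breathers only, neither 0.44 SD nor n = 24 would describe that test. All of this stands. A reader might infer that the SAP contradicts itself or that AHI is shown to be underpowered; the documents do not establish either.

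The reply does not rescue the word *greater*. Each of the favourable AHI readings that gives 81% to 99% power remains below the peak-flow power at 1.5 SD of the paired difference. If the word only meant that the other comparisons also exceed 80%, some readings would satisfy it, but the SAP gives nothing that selects them.

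Three other stronger readings should be set aside:

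- **Arithmetic error.** There is none: the chain from 30 to 24 to 16 reproduces, and the 1.5 SD statement is true as an inequality.
- **Sign test.** A reader might note that 16 of 24 gives a two-sided sign-test p of 0.15. The SAP names no such test and measures AHI as a quantity, so this is not its analysis.
- **Mouth against nose breathers.** The protocol says "We will also test the Varnum mouthpiece in nose breathers to serve as a control for the effectiveness of the Varnum mouthpiece", which may suggest a between-group test with less power. The SAP neither lists that test nor gives the split, so its power cannot be computed from the documents.

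**Conclusion.** The closing sentence states a power property that the documents do not support, and it is the only power statement for the first-listed main outcome. On the plain reading of the 67% (any reduction, normal paired changes, all 24 analysed together, paired t-test at two-sided 5%), AHI has an effect of about 0.44 SD and 54% power. The sentence is then false for AHI, which falls short both of 80% and of the more than 99.99% for peak flow at 1.5 SD of the paired difference.

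The shortfall against 80% is sensitive to the undefined response criterion and should not be presented as established. The claim of greater power is harder to meet, because it needs a cut-off above about 1.06 SD under normality (about 0.62 SD if the 1.5 is in raw units with uncorrelated nights). The peak-flow statement is correct but says little about what 24 pairs can detect.

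**What to change.** In the SAP's Power Calculations paragraph:

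1. Delete the closing sentence, or limit it to named comparisons with a stated effect, SD, test and alpha.
2. Replace the 1.5 SD statement with the effect detectable under the sponsor's own alpha, test and SD definition. If a two-sided 5% paired t-test is what is intended, this would read: *With 24 evaluable subjects, a paired t-test at two-sided 5% has 80% power to detect a difference of about 0.60 SD of the paired difference in peak inspiratory flow.*
3. State that AHI is not separately powered, unless an expected mean change and the SD of the paired change are supplied. If the 67% is kept, define response.

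This changes SAP wording only. N and the study procedures stay as they are. The cost is a less favourable power statement for AHI.
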